Real Time Assessment of Pre-oxygenation Utilizing End-tidal Oxygen Measurements versus Single Breath End-Tidal Oxygen Measurements in Healthy Volunteers

Short Title: Pre-oxygenation with Real Time End-tidal Oxygen Measurements versus Single Breath Measurements

Principal Investigator: [name]

Sponsors: None

Protocol Version 6  
March 20, 2025

NCT03840486

1. External (non-Emory) Collaborators: Not applicable
2. Precis/Abstract: A brief (usually 400 words or fewer) description of the study objectives, population, design, and outcome measures

Patients in the Emergency Department (ED) undergoing Rapid Sequence Intubation (RSI) are at risk for serious morbidity and mortality. In order to provide oxygen during the apneic period, it is common practice to provide pre-oxygenation prior to the start of the procedure with high flows of oxygen. Different methods of pre-oxygenation have been studied by taking a single breath end-tidal oxygen (EtO2) measurement with higher levels indicating more complete pre-oxygenation. However, there has not been any research examining methods of determining the quality of pre-oxygenation in real time.

This study examines the performance of a nasal cannula EtO2 measurement as compared to the gold standard of single breath end-tidal oxygen measurements in healthy volunteers. Study subjects will be placed on either a NRBM at different flow rates (15 LPM, 35 LPM, or Flush rate at 55 LPM) or a non-invasive ventilator facemask at various fractions of inspired oxygen levels (40%, 70% and 100%) for separate trials of 3 minutes at each flow rate or FiO2. At the end of each intervention, study subjects will perform a single breath end-tidal oxygen measurement by exhaling fully into a tube attached to an EtO2 sensor. In addition, a fourth trial arm will be done for both the NRBM and the NIV subjects that will correlate maximal readings from the real time EtO2 nasal cannula at the moment those maximal readings are obtained. The primary outcome will be the degree of correlation between real time EtO2 measurements (at the end of the three minute trial) and a single breath end-tidal oxygen measurement as measured by the k correlation coefficient, as measured for each trial. The secondary outcome will be the correlation of EtO2 between the nasal cannula sensor and the single breath sensor once stabilized at maximal readings.

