### **4. Study design and methods:**

#### **Study Procedure**

After screening procedures, participants will be asked to self report age, gender, height, and weight. Each participant will then perform a single breath EtO2 measurement to determine their own individual room air EtO2 measurement. They will also have a baseline measurement taken by the EtO2 nasal cannula sensor. Subjects will then be fitted for an appropriately sized non-invasive ventilator mask. Prior to the start of the study procedure, a nasal cannula EtO2 sensor will be placed on the participant's face with the non-invasive mask overlying the sensor. Participants will be randomized into each study arm after enrollment: the NRBM arm and the

NIV arm. Each participant will participate in the following treatment sequence. In addition to the study arm allocation, participants will be randomized to the order of their treatment sequence. After each treatment is completed, the participant will perform a single breath exhalation into a standard FeO2 sensor.

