**Group 1: NRBm Arm**

#1 NRBm at 15 LPM for 3 minutes

#2 NRBm at 35 LPM for 3 minutes

#3 NRBm at flush rate (55 LPM) for 3 minutes, the maximal reading at the end of this trial will be recorded, then the study subject will be allowed to rest until their EtO2 returns to their baseline, then they will be placed back on NRBm at flush rate, allowed to rise to the maximal reading of the previous step, then do a single breath exhaled EtO2 measurement

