**Group 2: NIV arm**

#1 NIV at 40% FiO2 for 3 minutes

#2 NIV at 70% FiO2 for 3 minutes

#3 NIV at 100% FiO2 for 3 minutes, the maximal reading at the end of this trial will be recorded, then the study subject will be allowed to rest until their EtO2 returns to their baseline, then they will be placed back on NIV at 100% FiO2, allowed to rise to the maximal reading of the previous step, then do a single breath exhaled EtO2 measurement

After each trial for #1 and #2 in each study arm, the study participants will be allowed to rest while breathing room air. Prior to the start of the next trial, each participant will perform a single breath EtO2 measurement to ensure they have returned to their baseline measurement. If the measurement is determined to be above their baseline, they will be allowed to rest until their single breath EtO2 measurement returns to its pre-intervention baseline. For trial #3 in each arm, the protocol will be followed as above so that the maximal reading can first be obtained to allow the completion of arm #3.

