**Risks and Discomforts**

The risks to study participants would be no more than minimal risk. The most common risk to study participants would be discomfort from using the NRBm or NIV masks. Participants may experience claustrophobia or discomfort from the higher flows of oxygen and air. If participants cannot tolerate the NRBm or NIV mask, they can discontinue the study at any time by removing the NIV mask themselves or asking a study investigator to remove the mask.

The study's original PI and the author of this protocol ([name]) has designed and helped to execute a similar study at his last institution that was similar in design to this study. This study involved placing healthy volunteers on a NIV mask with a nasal cannula

underneath the mask. All study subjects (64 in total) were able to tolerate the full study protocol without any adverse effects. This study has been published in a peer-reviewed journal. The IRB approval letter designated the study as “no more than minimal risk” with an expedited review is included in the e-IRB submission as an appendix.

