## **Statistical Analysis:**

## **Power calculation**

The study will be sufficiently powered to detect a 5% difference in ETO2. Five percent was chosen because it equates to approximately 30 extra seconds of safe apnea time in an 80 kilogram male (5% X 2,400 ml/O2 consumption at 250 ml/min). Based on a previous studies with similar study designs, we estimated that the standard deviation of ETO2 would be approximately 6.8%. Because six tests will be conducted, findings will be considered significant at the 0.0085 level (Sidak-corrected p value). These values were used to estimate the sample size required to achieve 80% power using Monte Carlo Simulations (10,000 samples) implemented in R v3.4.1. This analysis returned a total sample size of 104 (52 per arm). In order to account for an anticipated dropout rate of 10%, 116 participants will be enrolled. However, study enrollment will be terminated once 104 study subjects with complete data sets have been enrolled.

If a study participant cannot complete the entire protocol, their data will be excluded from the data analysis.

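### Excluding everyone who does not finish the protocol discards valid pairs from completed trials, although the primary correlation is assessed trial by trial (minor, cheap to improve)

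*Combined protocol and SAP*

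**What the plan says.** **The rule.** Power calculation: "If a study participant cannot complete the entire protocol, their data will be excluded from the data analysis". The same section and Participant selection set a target of 104 complete data sets (52 per arm), allow for 10% dropout and cap enrollment at 116.

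**The related criterion.** Exclusion criteria lists inability to tolerate the full course of non-invasive ventilation. The same section expects withdrawals to come mostly from intolerance of either mask.

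**The primary analysis.** The Precis defines the primary outcome as a correlation "as measured by the k correlation coefficient, as measured for each trial".

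**The readings.** Study Procedure states: "After each treatment is completed, the participant will perform a single breath exhalation into a standard" sensor. It also states that "participants will be randomized to the order of their treatment sequence". The Precis agrees on timing: "At the end of each intervention, study subjects will perform a single breath end-tidal oxygen measurement by exhaling fully into a tube". For trial #3, however, Group 1 mentions a single breath only after the participant is "placed back on NRBm at flush rate, allowed to rise to the maximal reading of the previous step, then do a single breath exhaled" measurement, and Group 2 is worded in the same way.

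**Evidence on tolerance.** Risks and Discomforts reports on an earlier study with an NIV mask: "All study subjects (64 in total) were able to tolerate the full study protocol without any adverse effects".

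**The concern.** A correlation computed for one setting needs one cannula reading and one single-breath reading per person at that setting. It needs nothing from that person's other settings. Someone who finishes one or two trials and then stops has supplied exactly what the primary analysis of those trials uses, and the rule removes it. The documents give no reason for doing so.

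Two things are at stake, both modest. The first is the loss of data already collected. The second is selection: if people leave because they cannot tolerate a mask and are replaced by people who can, the analysed set leans towards the tolerant. That could matter if intolerance goes with mask fit, leak or flow, but the documents do not say whether it does or which way it would move a correlation.

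The exclusion criterion adds to the problem. Eligibility is assessed before the procedures start, whereas tolerance of the whole course can only be known during them. The criterion also names NIV alone, so on its wording it does not reach the NRBM arm.

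**Working it through.** **Inputs from the documents:** 104 completers, 52 per arm; 10% dropout; cap of 116; three settings per arm; six tests; randomized order of settings; 0 of 64 intolerant in the earlier study.

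**Assumptions, because the documents are silent:** when participants stop; an even split of non-completers between arms; that the six tests are the six per-trial correlations (Power calculation does not define them and is framed around a 5% difference in EtO2); that the coefficient, called only k in the Precis, is Pearson.

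**1. The plan's own figure.** 104 / 0.9 = 115.6, rounded up to 116. This reproduces. Non-completers at the cap: 116 − 104 = 12.

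**2. Pairs kept under the rule.** 104 × 3 = 312.

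**3. Pairs discarded.**
- With 0 to 2 completed pairs per non-completer: 12 × 0 = 0 to 12 × 2 = 24, that is 0% to 24/312 = 7.7% of the pairs kept.
- If trial #3 has its own single breath before the repeat step, a participant who misses only that step could have three pairs: 12 × 3 = 36, and 36/312 = 11.5%.

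**4. Two illustrative stopping patterns.**
- Stopping equally likely in the first, second or third trial: mean (0 + 1 + 2)/3 = 1 pair each, so 12 pairs (12/312 = 3.8%), or 12/6 = 2 per test.
- Everyone stops at one setting in each arm: under random order that setting is equally likely to come first, second or third, so the mean is again 1 pair each and 12 in all. These fall on the other four tests, 12/4 = 3 each, with none at the problem setting.
- Upper case without a separate trial #3 breath: 24/6 = 4 per test. Ceiling with it: 36/6 = 6 per test.

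**5. Effect on precision.** Standard error on the Fisher-z scale = 1/√(n − 3).

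| Pairs per test | SE | Change from 52 |
|---|---|---|
| 52 | 1/√49 = 0.1429 | none |
| 54 | 1/√51 = 0.1400 | −2.0% |
| 55 | 1/√52 = 0.1387 | −2.9% |
| 56 | 1/√53 = 0.1374 | −3.8% |
| 58 | 1/√55 = 0.1348 | −5.6% |

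**6. If dropout is lower than planned.** For 0 of 64, the exact two-sided 95% upper limit is 1 − 0.025^(1/64) = 5.6%. At that rate 104/0.944 = 110.2, so 111 enrolled, about 7 non-completers and 7 × 0 = 0 to 7 × 2 = 14 pairs (14/312 = 4.5%). If nobody drops out, nothing is lost. The earlier study used an NIV mask, so it does not inform tolerance in the NRBM arm.

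**The case against.** The strongest case for the plan is that the rule is prespecified, simple and paired with replacement. Restricting to completers keeps the same people at every setting within an arm, which is a legitimate aim. For NIV intolerance the rule also applies a listed exclusion criterion, so changing the Power calculation sentence alone would set the two sections against each other. Finally, the consent pages are not in the available text, so it cannot be checked whether readings taken before a withdrawal may be used.

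Much of this stands. The same-people comparison is worth keeping, the exclusion criterion has to be dealt with together with the analysis rule, and use of the pairs must depend on consent. None of it gives a reason why a pair that has been properly measured should not enter the analysis of its own trial.

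A reader might infer three stronger claims, which the documents do not support:
- **That the rule leaves the trial short of participants.** It does not. Enrollment continues to 104 full data sets within the cap of 116, so at the planned dropout the planned 52 per arm is reached.
- **That the rule biases the correlation in a known direction.** Nothing in the documents links intolerance to agreement between the two readings. Keeping observed pairs would also remove the selection only in part, since a trial stopped midway still yields no pair.
- **That the rule contradicts the Missing Data section.** The two can be read together, with imputation serving readings lost in people who finished.

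**Conclusion.** The point holds as a minor, low-cost improvement. The rule discards pairs that are valid for a per-trial analysis, while the planned precision stays intact. At the planned dropout the loss is 0 to 24 pairs against 312 kept (0% to 7.7%). The ceiling of 36 (11.5%) applies only if a single breath is taken in trial #3 before the repeat step. The likely gain is a Fisher-z standard error about 2% to 4% smaller, and 5.6% at most.

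These precision figures rest on 12 non-completers split evenly between arms, on the assumed stopping patterns, on a Pearson coefficient, and on reading the six tests as per-trial correlations. The tolerance seen in the earlier study suggests that the true gain could be zero. The central observation, that completed pairs are dropped without need, depends on none of these assumptions beyond someone stopping after at least one completed trial. Nor does it depend on how the figure of 104 was derived.

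**What to change.** Replace the sentence in Power calculation with:

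> Every trial in which both the cannula and the single-breath reading were obtained enters the analysis of that trial, whether or not the participant finished the remaining trials, as far as consent allows.

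Keep the completers-only analysis as a sensitivity analysis. Reconcile the exclusion criterion on tolerating NIV with this sentence, so that it does not remove pairs already measured. This concerns only which data are analysed, not how intolerance is managed.

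**Cost.** Edits to two sections and a check of the consent wording. The target of 104 completers, the cap of 116 and the study procedures are unchanged. The one statistical downside is that slightly different people may contribute at different settings, which the completers-only sensitivity analysis addresses.

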## **Missing Data**

In the event of substantial missing data, data will be imputed using a multiple imputation procedure. The type of procedure and the number of imputed data sets will be determined by the amount of missing data and the pattern of missingness.

## **Data and Safety Monitoring and Reporting**

Since this study does not involve any more than minimal risk to study participants, there will not be a pre-planned interim monitoring or data analysis.

While significant side effects and reportable events are not anticipated from the study, any significant side effects requiring medical treatment or reportable events will be immediately reported to the Emory IRB by the study's primary investigator.

## **Confidentiality**

Study participant's inclusion in the study will be kept confidential. Study subjects will be assigned a study subject number at the beginning of the study. Study subjects will be asked to self report their age, sex, height, and weight which will be recorded onto the data forms. These data forms will not contain any other personally identifiable study subject information. Data from these forms will be transcribed into a secure database (REDCAP).

Video recordings of the monitor readings will be immediately deleted after they are transcribed onto the data forms, which will occur immediately at the end of each study procedure. Study subjects will be consented for these video recordings prior to the study. If they do not consent to these video recordings, they will not be allowed to enroll in the study.

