## **Data collection and storage procedures**

All data will be collected on a standardized data collection form and entered into a secure database program (REDCAP) for data analysis. The PI, AI, and any study research personnel who assist with the study will have access to the database. Each subject will be assigned a subject number according to the order in which they were enrolled into the study. The data will be stored for a maximum of 3 years to ensure the ability to publish study results. After the data is stored for 3 years, it will be deleted. In addition, the study investigators will video record the screens displaying the EtO2 data to allow accurate data transcription. Once the data has been transcribed, these videos will be deleted. These videos will solely be focused on the video screen and will not capture the study subject’s face or any other identifying features. These videos will only be identified by the assigned study subject number and will not contain any other identifying information.

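### The end-of-trial cannula value is not defined and its reader is not masked, so knowledge of the reference breath could influence the primary comparison

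*Combined protocol and SAP*

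**What the plan says.** The Precis/Abstract defines the primary outcome as the correlation between "real time EtO 2 measurements (at the end of the three minute trial) and a single breath end-tidal oxygen measurement", assessed for each trial. No section says which breath, second or averaging window supplies the cannula value.

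The Study Procedure section places the reference after the treatment: "After each treatment is completed, the participant will perform a single breath exhalation into a standard" sensor.

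The Data collection and storage procedures section says that "the study investigators will video record the screens displaying the EtO 2 data to allow accurate data transcription". The Confidentiality section times the transcription: "they are transcribed onto the data forms, which will occur immediately at the end of each study procedure". It also says what happens to the source: "Video recordings of the monitor readings will be immediately deleted after they are transcribed onto the data forms".

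The plan names no masked or independent reader and fixes no order for entering the two values. It does not say who transcribes, or whether the cannula value is also noted live.

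Trial #3 works differently in both arms. In the first run "the maximal reading at the end of this trial will be recorded". The participant then rests, is brought back up to that reading, and gives the single breath.

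**The concern.** This is a comparison of an index measurement with a reference that the protocol calls the gold standard. A real-time sensor followed for three minutes gives many values, and one must be chosen or computed for the pair. Three features combine here: the choice is not specified, it can be made after the reference is available, and the source is then destroyed.

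If the person choosing knows the reference, any leaning towards it pulls the pair together and raises the correlation. The Introduction hypothesizes that the cannula is reliable, so the error would run in the hoped-for direction. At stake is whether clinicians are told that the sensor follows the reference more closely than it does. The point concerns the readings at the end of three minutes, which feed the primary outcome.

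**Working it through.** **Order of events as written**

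1. Treatment runs for three minutes while the screens are filmed (arm descriptions; Data collection and storage procedures).
2. The participant gives the reference breath after the treatment (Study Procedure).
3. Values are transcribed from the video at the end of each study procedure (Confidentiality). The term is not defined. Whether it means one trial or the whole session, step 3 falls after step 2.
4. The video is deleted (Confidentiality; Data collection and storage procedures).

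Nothing between steps 2 and 3 keeps the reference from the reader, and nothing after step 4 allows a second reading.

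**Trial #3 repeat run**

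The maximal reading is the target for the repeat run, so it must be known before the repeat breath. That cannula value is fixed first, and the concern does not reach it.

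**Illustrative size**

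The plan has no figure of its own to reproduce on this point.

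- From the plan: SD of EtO2 6.8 points (Power calculation).
- Assumed: breath-to-breath cannula SD b of 2 to 5 points; three candidate breaths; a reference without error; no other disagreement between devices. The documents give none of these.
- Pearson r is used for illustration. The Precis/Abstract names a k correlation coefficient without defining it.

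With a fixed rule, r = 6.8 / √(6.8² + b²), and the 95% half-width of the difference is 1.96·b.

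- b = 2: 6.8 / √(46.24 + 4) = 0.96
- b = 5: 6.8 / √(46.24 + 25) = 0.81; half-width 9.8 points

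If the nearest of three breaths is always taken, b² is multiplied by c = ∫₀^∞ 2x[2(1 − Φ(x))]³ dx = 0.193.

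- b = 2: 6.8 / √(46.24 + 0.77) = 0.99
- b = 5: 6.8 / √(46.24 + 4.82) = 0.95; half-width 1.96 × √4.82 = 4.3 points

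If this happens in 25% of readings (also assumed), b² is multiplied by 0.75 + 0.25 × 0.193 = 0.798.

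- b = 2: 6.8 / √(46.24 + 3.19) = 0.97
- b = 5: 6.8 / √(46.24 + 19.95) = 0.84; half-width 8.8 points

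Simulation with 400,000 draws gives the same figures.

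| Assumed breath SD | Fixed rule | 25% selected | Always nearest of three |
|---|---|---|---|
| 2 points | r 0.96 | r 0.97 | r 0.99 |
| 5 points | r 0.81 | r 0.84 | r 0.95 |

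**Second model**

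This adds subject-level disagreement between devices (SD 2, 4 or 6), with breath SD 1, 2 or 3, three or five candidate breaths, and selection in every reading. With disagreement SD 4, breath SD 2 and five breaths, r goes from 0.837 to 0.934 and Lin's concordance coefficient from 0.824 to 0.931. Over the grid the gain in r runs from about 0.03 (0.950 to 0.975) to 0.15 (0.713 to 0.865). These too are upper bounds.

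**The case against.** The strongest reply is that the documents show an absence of safeguards, not a biased reading. A reader might infer that the transcriber will already have seen the reference and that the cannula value comes only from the video. The plan says neither. It does not identify the transcriber and does not rule out a live note. This stands, and the point is limited to what the workflow leaves open.

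A reader might also infer that the comparison at maximal readings is compromised. It is not: the trial #3 target has to be read live, before the repeat breath.

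Third, the documents do not say that the cannula signal fluctuates between breaths. The Introduction says only that high flows could distort it, and a steady distortion would give a reader nothing to choose between. The Precis/Abstract also names a time point, which narrows the choice. Both remarks are fair. They make the size uncertain and possibly small, but a time point without a breath or window rule still leaves a choice.

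Fourth, one might argue that selection would also hide a constant offset between devices. The stated endpoint is a correlation, which a constant offset does not change, so that argument is not used here.

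Finally, taking the nearest breath every time is an extreme. This stands as well, which is why the 25% case is shown beside it.

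**Conclusion.** The point holds for the primary, end-of-three-minutes comparison only. The cannula value is undefined, its reader is unmasked, and on the written order it is transcribed after the reference, with no later check possible. Knowledge of the reference could therefore inflate the correlation.

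The documents do not allow the size to be computed. On the assumed breath SDs, the gain in r ranges from about 0.01 (SD 2, a quarter of readings selected) to about 0.15 (SD 5, every reading selected). The upper figure is a bound, not an expectation. With partial selection the effect is modest. The change is worth making because it is cheap and protects the only primary outcome. Nothing here shows that inflation will occur.

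**What to change.** In the Study Procedure and the Data collection and storage procedures sections:

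- Define the primary cannula value in advance as the value displayed at exactly 3:00, or as the mean over a pre-set final window.
- Call it out and write it on the form before the single breath is performed.
- Use the video only to verify that value at that timestamp, and allow no change based on any other breath.

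Align the Confidentiality wording, so that the video is deleted after this verification. Fixing the order of fields on the form would not be enough on its own, because it does not blind a reader who was in the room for the single breath. Recording the value before that breath does not depend on blinding anyone.

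The cost is a few sentences and one form field, with no extra participants or readers. The downside is that a single fixed-time value may catch an aberrant breath, so the reported correlation may be slightly less favourable. A pre-set window reduces this.
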